Aim 1: The primary study aim is to improve patient satisfaction, education, and patient reported outcome measures after urethroplasty. All enrolled patients will complete a urethroplasty specific PROM survey, the Urethral Stricture Symptom and Impact Measure (USSIM), as well as the Patient-Reported Outcomes Measurement Information System 29-item profile (PROMIS-29 v2.0) preoperatively, two weeks after catheter removal, and again at three months after surgery. Three months after surgery patients will also complete a decision regret scale. Patients enrolled with the application will complete an overall assessment of GetWell Loop at the end of the study.

Aim 2: The second aim of the study is to decrease patient phone calls and messages due to improved patient education and troubleshooting provided by the interactive guide. Prospective chart review will be conducted on all patients enrolled in the study to evaluate the number of MyChart messages and phone calls.

Aim 3: The final aim is to decrease emergency department visits and improve postoperative outcomes. Postoperative complications will be rated on the Clavien-Dindo classification. Emergency department visits will be assessed by prospective chart review and patient interviews. Overall healthcare costs will be extrapolated based on the outcomes of emergency department visits.

STU#:

BACKGROUND:

Urethral stricture disease is fibrosis within the urethra that leads to significant narrowing of the urethral lumen. Strictures can occur from traumatic, iatrogenic, inflammatory, infectious, or idiopathic etiologies. Urethroplasty is the most effective and durable treatment for urethral stricture. However, perioperative care for urethroplasty is complex. Preoperative counseling can be challenging as the anatomy can be quite foreign to the layperson, thus the description of the procedure as well as the associated risks and benefits can be difficult to understand. Indeed, this appears to be a universal problem within surgery and multiple studies have highlighted poor patient comprehension and recall from standard preoperative counseling. Preoperative care can also be cumbersome, with patients in urinary retention managed with a urethral Foley requiring conversion to a suprapubic tube to allow for a period of urethral rest. Preoperative urine cultures are also required, and many patients will have a positive urine culture requiring antibiotic treatment prior to surgery.

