Within urology, Belarmino et al conducted a feasibility study for the use of a mobile health application after robotic assisted radical prostatectomy. 20 patients were recruited preoperatively and completed a baseline PROM survey. Their application did not include preoperative counseling but was rather focused on postoperative care including reminders to perform Kegel exercises, ambulate, and hydrate. Men were asked to complete the same PROM survey weekly after catheter removal. All respondents reported that the push reminders were useful and 93% found the app easy to use. Importantly, they also found that the PROM response rates were significantly higher than those for mail and email surveys and comparable to phone surveys.

Metcalfe et al conducted a study in 2019 implementing an application for cystectomy perioperative monitoring. 20 patients were enrolled in the pilot trial and given a tablet with the preloaded application as well as a step monitor and vital sign equipment. Their study did include 14 preoperative educational videos on topics such as "Ileal conduit versus Neobladder" and "Comprehensive Care Pathway". All participants viewed the videos and 93% averaged more than one view per video.

Notably, both these studies were feasibility studies and no study within urology thus far has evaluated the effectiveness of these mobile health applications for patient education or compared them to the standard of care.

We will conduct a prospective, randomized controlled trial assessing the effectiveness of a mobile health application on perioperative outcomes and patient satisfaction for patients undergoing urethroplasty.

STUDY ENDPOINTS:

Primary endpoint: Improve patient satisfaction, education, and patient reported outcome measures after urethroplasty.

Secondary endpoint: decrease patient phone calls, chart messages, ER visits, and improve complication rates.

STUDY INTERVENTION(S) / INVESTIGATIONAL AGENT(S):

We will conduct this study in partnership with GetWell Loop, a mobile medical application designed by GetWell Network. We plan to work with GetWell to develop a custom build plan for a urethroplasty specific perioperative patient education application. Eligible patients will be randomized to one of two arms: standard care pathway and the mobile health (mHealth) pathway.

GetWell Loop MMA details:

Purpose of the app:

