We will conduct a prospective, randomized controlled trial assessing the effectiveness of a mobile health application on perioperative outcomes and patient satisfaction for patients undergoing urethroplasty over a 12-month period. Experimental design including inclusion and exclusion criteria is outlined in **Figure 1**. Patients will undergo a two-stage consent process and a non-blinded randomization technique. Our institution performs 80-100 urethroplasty procedures a year. Our goal is to enroll 80 patients, 40 patients per arm. To reduce attrition, financial incentive will be provided after completion of the final study survey (obtained at three months postoperatively) with a \$100 Amazon gift card. If enrollment is significantly lower than expected, we will have continued institutional support and funding to extend our enrollment period. We will partner with GetWell Loop, an organization that has been well established within our hospital system, to develop a custom build for our application. We will evaluate our outcomes based on an intention-to-treat and per-protocol analysis and will define statistical significance as a p-value <0.05.

STU#:

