The duration of the study is 12 months, however participation for each patient will be from time of their clinic visit where they sign up for urethroplasty and are recruited into the study to 90 days following their surgery. We plan to enroll 80 patients (40 per arm) and estimate this will take the entire year given our current clinical patient volume. We plan to start enrolling patients in August 2023 in anticipation of initiating launch of the application in August 2023. We anticipate completion of the participation in the study around July 2024.

INCLUSION AND EXCLUSION CRITERIA

Eligible patients include those over 18 years old who have a urethral stricture and are undergoing urethroplasty surgery with [name] at Northwestern Memorial Hospital. Exclusion criteria consists of patients without mobile phone capability to utilize GetWell Loop, physical or cognitive impairment precluding usage of a mobile phone or answering questionaries, and inability to consent to the study.

VULNERABLE POPULATIONS

PARTICIPANT POPULATION(S)

Accrual Number:	Category/Group: (Adults/Children Special/Vulnerable Populations)	Consented: Maximum Number to be Consented or Reviewed/Collected/Screened	Enrolled: Number to Complete the Study or Needed to Address the Research Question
Local	Adults	120	80
Study-wide		120	80
Total:		120	80

STU#:

RECRUITMENT METHODS

Patients scheduled to undergo urethroplasty surgery will initially be approached in clinic and given information regarding the study design and goals. All patients regardless of race/ethnicity/gender/socio-economic status will be approached. If patients have transportation issues and cannot make it to an in-person visit, a virtual visit can be offered instead, and patients can be recruit via this approach. If interested, the patient will then sign a generalized consent form enrolling them into the study. Eligible patients will then be randomized to one of two arms: standard care pathway and mHealth pathway. We will attempt to match patients based on demographics to have even distributions between the groups. We will utilize non-blinded block randomization technique due to the nature of the intervention pathway and need for continuous enrollment.

COMPENSATION FOR PARTICIPATION IN RESEARCH ACTIVITIES

To reduce attrition, financial incentive will be provided after completion of the 3-month follow up surveys with a \$100 Amazon gift card.

WITHDRAWAL OF PARTICIPANTS

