Once the participant is enrolled, we will adhere to the IRB standard requirements for non-English speaking participants and obtain certified translations of the documents related to the study.

PROTECTED HEALTH INFORMATION (PHI AND HIPAA)

This research study will involve the collection of Protected Health Information (PHI) from the patient's electronic medical record (EMR). PHI will also be created in this study: the

STU#:

questionnaires participants will be asked to complete will collect health information which may otherwise not be captured in the EMR.

HIPAA Authorization will be obtained from all participants. The following information may be collected for each participant:

- Name
- Medical Record Number
- Telephone number
- Email address

QUALIFICATIONS TO CONDUCT RESEARCH AND RESOURCES AVAILABLE

Persons involved in this study have experience with patient care and the handling of sensitive information. [name] is an assistant professor of urology here at Northwestern who specializes in reconstructive urology. Other staff, including residents, research coordinators, medical students, and nursing will have appropriate oversight by the PI. Staff are familiar with study sites at Northwestern Memorial Hospital / Northwestern Medical Group and Northwestern University culture. Facilities for conducting this research are adequate, including clinic space, secure computer workstations, and availability of access to other Northwestern University resources including the EDW. All persons assisting with research will be adequately informed regarding the protocol and research procedures and will have access to both text of the protocol and an “open-door policy” to promote a culture of questions, transparency, and communication.

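### Aim 2's contact count rests on chart review under open allocation with no masking described; one pre-written, arm-neutral count would remove an avoidable risk of bias (minor)

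*Protocol*

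**What the plan says.** The Protocol names the method of counting twice, under OBJECTIVES (Aim 2) and again under PROCEDURES INVOLVED: "Prospective chart review will be conducted on all patients enrolled in the study to evaluate the number of MyChart messages and phone calls". The aim carries a direction: "The second aim of the study is to decrease patient phone calls and messages due to improved patient education and troubleshooting". STUDY ENDPOINTS ranks these contacts as secondary: "Secondary endpoint: decrease patient phone calls, chart messages, ER visits, and improve complication rates".

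Allocation is open. PROCEDURES INVOLVED states: "Patients will undergo a two-stage consent process and a non-blinded randomization technique". RECRUITMENT METHODS gives the reason: "We will utilize non-blinded block randomization technique due to the nature of the intervention pathway and need for continuous enrollment". The target is stated as follows: "Our goal is to enroll 80 patients, 40 patients per arm".

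The section on qualifications and resources lists "availability of access to other Northwestern University resources including the EDW". It does not expand the abbreviation (read here as the institution's data warehouse) or link it to Aim 2. Under Participant/user support, app users may put care questions to providers through GetWell Loop as well as through MyChart. The Aim 2 count names MyChart and telephone only.

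**The concern.** Counting contacts from a chart can require small decisions: whether a thread is one contact or several, whether a scheduling message counts, and who started the exchange. The review is prospective, so these decisions would fall during follow-up. The same team trains app-arm patients in clinic, and one of its lead members receives notifications from the app's messaging portal, so staff can know the arm. If they also make the count, decisions could lean towards the stated hypothesis.

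At stake is the whole of Aim 2, and with it the calls and messages among the secondary endpoints. The protocol fixes the source of the count as chart review, and that choice is open to improvement whatever a statistical analysis plan may add. Masking is also easiest to secure before counting starts.

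**Working it through.** **No plan figure to reproduce.** The protocol gives no contact rate, dispersion, expected reduction or power for Aim 2. Only the allocation can be checked: 2 × 40 = 80.

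**Inputs.** From the protocol: 40 per arm and significance at p < 0.05. Assumed: a two-sided test, a mean of m contacts per patient in the control arm (3, 5 or 10), negative binomial dispersion k (0, 0.5 or 1.0; variance m + k·m²), no true effect, and a share u of contacts missed in the app arm only.

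**Formula.** For a Wald test on the log rate ratio, with m₂ = m(1 − u):

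- SE² = (1/m + k)/40 + (1/m₂ + k)/40
- P(false significant reduction) = Φ(|ln(1 − u)|/SE − 1.96)
- Smallest significant observed reduction ≈ 1 − exp(−1.96 × SE₀), where SE₀ = √(2(1/m + k)/40)

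**Worked case: m = 5, k = 0.5, u = 10%.** Here m₂ = 4.5, so SE² = 0.700/40 + 0.722/40 = 0.0356 and SE = 0.189. |ln 0.9| = 0.105, and 0.105/0.189 = 0.56. Φ(0.56 − 1.96) = 8.1%. In contacts, this is 20 missed out of 40 × 5 = 200 in the arm. For the threshold, SE₀ = √(2 × 0.7/40) = 0.187 and 1 − exp(−0.367) = 30.7%.

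**All settings** (with u = 0 the chance is 2.5% throughout):

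| m | k | u = 5% | u = 10% | u = 20% | Smallest significant reduction |
|---|---|---|---|---|---|
| 3 | 0 | 5.8% | 12.2% | 37.1% | 22.4% |
| 3 | 0.5 | 4.4% | 7.4% | 18.6% | 33.0% |
| 3 | 1.0 | 3.9% | 6.0% | 13.4% | 39.7% |
| 5 | 0 | 7.3% | 17.5% | 55.7% | 17.8% |
| 5 | 0.5 | 4.6% | 8.1% | 21.5% | 30.7% |
| 5 | 1.0 | 4.0% | 6.3% | 14.5% | 38.1% |
| 10 | 0 | 10.7% | 30.5% | 84.5% | 12.9% |
| 10 | 0.5 | 4.8% | 8.8% | 24.7% | 28.8% |
| 10 | 1.0 | 4.1% | 6.5% | 15.5% | 36.9% |

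The rows with k = 0 (pure Poisson) are a limiting case in which all patients have the same underlying contact rate.

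**Check by simulation.** Gamma-Poisson counts with mean 5 to 10 and shape 1 to 4 (k = 1/shape, so 1.0 to 0.25) were compared by a t-test on square-root counts, with 20,000 trials per setting. Across two runs, false significant reductions occurred in 2.4–2.8% of trials with no undercount, 5.9–11.4% with a 10% undercount and 12.4–35.8% with a 20% undercount. The two methods agree in order of size.

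**In-app messages.** A contact that moves to an uncounted channel acts like a missed one. If half of app-arm contacts moved into GetWell Loop, the same formula gives a false significant reduction in 72% to 97% of trials (k 0.5 to 1.0, m 3 to 10). The protocol gives no basis for that share. The figure shows only that masking the MyChart and telephone count would leave this gap open.

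**The case against.** The strongest reply is that the protocol never says the count is manual or that the people making it know the arm. The term non-blinded describes the randomisation technique, chart review does not exclude an electronic pull, and masking and counting rules may sit in an analysis plan or data manual. This stands as far as it goes: counting by staff who know the arm is a possibility that the text leaves open, and the absence of a detailed counting rule is not itself a fault.

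A reader might also infer that small counting differences would by themselves deliver the hypothesised reduction. The documents do not support that. They state no size for the reduction, and with overdispersed counts an observed difference of about 29% to 40% is needed for significance (about 13% to 22% under pure Poisson). With a 10% undercount, about nine trials in ten would still show no false reduction.

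Nor would such a bias be beyond detection. A count made from the chart rests on entries recorded there, so it can be repeated later by someone masked to arm. Recorded messages also leave less room for judgement than a rated outcome.

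Finally, a data-warehouse query is not a complete answer. The protocol does not show that the EDW holds message and call records, and a query would inherit any difference in how clinic staff log calls. These replies limit the point and shape the remedy. They do not remove the gain from an arm-neutral count.

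**Conclusion.** The point holds as a minor, inexpensive improvement. A secondary endpoint with a hoped-for direction is to be counted by chart review under open allocation, with no masking described. If counters know the arm and miss 10% of app-arm contacts, the chance of a false significant reduction rises from about 2.5% to about 6–11%. This assumes 40 analysed per arm, no true effect, 5 to 10 contacts per patient and overdispersion. The contact rates, the dispersion and the undercount itself are all assumptions, and nothing in the protocol shows that an undercount would occur. With identical counting in both arms, the chance returns to 2.5%.

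**What to change.** In OBJECTIVES (Aim 2) and in the matching paragraph of PROCEDURES INVOLVED, replace the open chart-review count with one pre-written counting rule:

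- It defines a contact and applies identically to both arms over the same window. The window needs one definition, because STUDY TIMELINES runs participation to 90 days after surgery, while DATA MANAGEMENT AND CONFIDENTIALITY gives 90 days of follow-up after enrolment.
- It runs once, after the last follow-up, as a single EDW query if the EDW is confirmed to hold these records. Otherwise it is applied to a record extract without arm labels.
- The arm is merged only after the counts are locked.
- It says how care messages sent through GetWell Loop are handled, for example by reporting the count with and without them.

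Chart reading can still be used to describe reasons for contact.

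The cost is a wording change and some query or extraction work. Some unrelated contacts will be counted. Questions about the app itself sent by MyChart would arise almost only in the app arm, so the rule should say whether they count. Differences in how clinic staff log calls would remain.

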Postoperatively, all patients will have a urethral catheter for 1-4 weeks depending on the repair. More complex strictures may require buccal mucosa graft and even local tissue flaps such as a gracilis muscle flap. At our institution, many patients undergo same-day discharge or are admitted for one night, limiting time for in person postoperative teaching. These attributes underscore the importance of patient education as they may generate patient questions and anxiety.

Studies have shown a discordance between patient and physician perception regarding success after urethroplasty surgery. As a result, there has been growing interest in patient reported outcome measures (PROM) as a marker for success after urethroplasty. However, PROM surveys are time and resource intensive to capture.

Mobile health applications have the potential to improve patient education, quality of life, and postoperative outcomes after surgery. They are also a way to capture PROM in a more reliable and efficient manner. Within the field of urology, mobile health applications have been created for perioperative prostatectomy and cystectomy care. However, no mobile health application has been created for urethroplasty, and there has not been a randomized controlled trial regarding their efficacy within this space.

Mobile health applications are low-cost, accessible, and scalable resources that have been gaining popularity in recent years. Most patients own a smartphone regardless of socioeconomic status. Most mobile health applications are geared towards chronic illness and primary prevention, however interest in surgery specific mobile health applications is growing. A survey regarding willingness to use mobile health applications after a hypothetical surgery scenario conducted on 800 New York State residents by Abelson et al, found that 80.6% of respondents reported willingness to wear a tracker on their wrist and 74.3% were willing to fill out a daily survey after surgery. Notably, older respondents were less likely to own a smart phone but had similar willingness to participate in mobile health technologies if they did own one.

STU#:

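### Allocation seeks balance on demographics only; stratifying by planned repair complexity would be a cheap, modest gain in precision with 40 patients per arm

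*Protocol*

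**What the plan says.** Recruitment Methods in the Protocol fixes the allocation in two sentences. On balance: "We will attempt to match patients based on demographics to have even distributions between the groups". On method: "We will utilize non-blinded block randomization technique due to the nature of the intervention pathway and need for continuous enrollment". The demographic factors are not listed, and no stratum or block size is given. Procedures Involved sets the size: "Our goal is to enroll 80 patients, 40 patients per arm".

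The Background describes how patients differ. It says that "all patients will have a urethral catheter for 1-4 weeks depending on the repair", and continues: "More complex strictures may require buccal mucosa graft and even local tissue flaps such as a gracilis muscle flap". After noting that many patients go home the same day or after one night, it concludes: "These attributes underscore the importance of patient education as they may generate patient questions and anxiety".

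Eligibility does not restrict the type of repair. Aim 2 counts calls and MyChart messages. Aim 1 times its first postoperative PROM survey from catheter removal. No part of the text names repair type, graft or flap use, or expected catheter time as a factor to balance. Figure 1 is not available in the copy reviewed; the text says it includes the inclusion and exclusion criteria and mentions no strata.

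**The concern.** The Protocol makes one balancing effort and directs it at demographics. It states no link between demographics and the outcomes; its one remark on age concerns owning a smartphone and willingness to use mobile health tools. Repair complexity does have a stated link: to catheter time directly, and to patient questions as one of several attributes.

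Two outcomes are exposed on the Protocol's own account. Patient questions become the contacts counted in Aim 2. Catheter time also determines when the first postoperative PROM survey is taken, so arms that differ in repair mix would be surveyed at different average times after surgery. Effects on emergency visits and complications are plausible, but the Protocol does not state them.

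With 40 patients per arm, a visible imbalance in repair mix is common. It would be hard to argue away afterwards, and part of the outcome variance would go unused.

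**Working it through.** **Inputs from the Protocol.** 80 patients, 40 per arm; block randomisation with no stratum named; catheter for 1-4 weeks; first postoperative PROM survey 2 weeks after catheter removal.

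**Assumptions (not in the Protocol).** Share of complex repairs p = 30-50%. Gap g between complex and simple repairs on an outcome = 0.3-0.8 within-group SD. Block size 4 in the simulations.

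**The Protocol's own figure.** The 80 cannot be reproduced, because no effect size, SD, event rate or power is given. For scale only: 40 per arm detects (1.96 + 0.84) × √(2/40) ≈ 0.63 SD with 80% power, two-sided 5%.

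**Step 1: timing of the PROM survey.** 1 + 2 = 3 weeks to 4 + 2 = 6 weeks after surgery.

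**Step 2: chance of imbalance.** The number of complex repairs in each arm is taken as Binomial(40, p). The second set of columns simulates unstratified blocks of 4 (10,000 trials for each p).

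| p | Binomial: ≥10 points | Binomial: ≥20 points | Blocks of 4: ≥10 points | Blocks of 4: ≥20 points |
|---|---|---|---|---|
| 0.3 | 39.3% | 6.7% | 39.4% | 6.4% |
| 0.4 | 42.4% | 8.6% | 41.6% | 8.0% |
| 0.5 | 43.3% | 9.3% | 43.0% | 9.3% |

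Ordinary blocking therefore does not help: it balances the arm sizes, not the repair mix. If the total number of complex repairs is instead fixed at 24, 32 or 40 of 80 and split 40/40 (hypergeometric), the figures are 47-50% and 9-12%. They are higher because with an even total the counts in the two arms can differ only by even numbers.

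**Step 3: the same simulation with repair type as a two-level stratum.** None of the 10,000 trials at any assumed share reached a 10-point difference.

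**Step 4: effect of a 20-point imbalance.** Shift in the unadjusted arm difference = 0.20 × g. This gives 0.20 × 0.3 = 0.06 SD to 0.20 × 0.8 = 0.16 SD. The standard error of the arm difference is √(2/40) = 0.22 SD.

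**Step 5: value of adjustment.** R² = g²p(1−p) / [1 + g²p(1−p)], and the equivalent extra sample is 80/(1−R²) − 80 = 80 × g²p(1−p).
- g = 0.3: 80 × 0.09 × 0.21 = 1.5 (p = 0.3) to 80 × 0.09 × 0.25 = 1.8 (p = 0.5); R² about 0.02.
- g = 0.8: 80 × 0.64 × 0.21 = 10.8 to 80 × 0.64 × 0.25 = 12.8; R² 0.12 to 0.14.

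The gain is therefore roughly 2 to 13 patients.

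**The case against.** The strongest reply is that nothing here is invalid. Randomisation without a prognostic stratum is sound, and the standard error already allows for chance imbalance. That stands. A reader might infer that the omission biases the trial or inflates the type I error; it does neither on average. Even a 20-point imbalance, seen in about 7-9% of trials under the assumed shares, moves the arm difference by less than one standard error (0.06-0.16 against 0.22 SD).

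A reader might also infer that the Protocol says repair complexity drives questions, anxiety, complications and PROMs. It does not. The wording is that "they may generate patient questions and anxiety", short hospital stay is among the attributes meant, and the paragraph argues for patient education rather than prognosis. Only catheter time is said to depend on the repair.

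Larger effects are easy to produce. If complex repairs doubled contacts, 50% against 30% complex would give 1.5/1.3, a 15% difference; an R² of 0.1-0.2 would be worth 9-20 patients. The documents support neither premise, and that R² range needs a gap of about 0.67-1.1 SD.

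The gain in Step 5 comes from adjustment, which may be specified in an SAP that is not shown, so its absence here is no fault. The allocation scheme is different, because the Protocol itself fixes it. Nor does the text say that the repair is settled at sign-up, or that graft or flap use separates long from short catheterisation. The proposed stratum is a reasonable proxy, not one the Protocol establishes.

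**Conclusion.** The point holds as a modest improvement in precision. Demographics are the only named balancing basis, and nothing else in the text balances repair type. The Protocol itself ties repair to catheter time and, as one attribute among several, to the questions that feed Aim 2. Under an assumed 30-50% share of complex repairs, differences of 10 points or more arise in about 39-43% of trials and of 20 points or more in about 7-9%. Under an assumed gap of 0.3-0.8 SD, a 20-point imbalance moves the arm difference by 0.06-0.16 SD and adjustment is worth roughly 2-13 patients. The share, the gap and the block size are all assumptions.

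The documents do not support calling the present scheme biased, nor saying that demographics must be abandoned. The case for acting is that the change costs little and that the stratum cannot be added once patients have been allocated.

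**What to change.** In Recruitment Methods, stratify the block randomisation by one binary factor: planned graft or flap repair, yes or no. Record it before the allocation is revealed. Include the stratum as a covariate in the analyses of PROMs and contacts, and of emergency visits and complications where event counts allow. Replace the attempted demographic matching with demographic covariates, so that demographics are still addressed.

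The cost is one field at randomisation and one model term. There are two cautions. The planned repair may differ from the one performed, so the planned category must be used throughout. The category must also be locked before assignment, because allocation is unblinded and a team that could choose the stratum after seeing the next assignment could steer patients.
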